4.3. Prior/Concomitant Medications

All medications will be coded using World Health Organization (WHO) Drug Dictionary by active ingredient and WHO anatomical therapeutic chemical (ATC) classification of ingredients.

A prior medication is defined as any medication taken from the last visit of the double-blind study through the signing of informed consent form at Screening A in this study. A concomitant medication is any medication starting on or after the informed consent form at Screening A is signed for this study.

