- ^b Day 71 Visit is in double-blind study (EN3835-302/303).
- ^c Visit 1 Day 180 is in study EN3835-304; approximately 180 days after Day 71 of double-blind study. A subject who terminates study participation between Day 71 and Day 180 will have an Early Termination Visit that includes the Assessments listed for Visit 1 Day 180.
- ^d If the composite (CR-PCSS and PR-PCSS) ratings worsen by at least 1-level composite response ratings at Day 180 Visit or at a subsequent unscheduled unblinding visit for a subject that had a 2-level composite improvement at Day 71 of the double-blind study, an additional visit should be scheduled 14 days (\pm 5 days) later to confirm reduction of response, via re-assessment with the CR-PCSS and PR-PCSS.
- ^e Depending on the date of unblinding of subject's treatment in EN3835-302/303; investigators, subjects, and site personnel may be unblinded at Day 180 Visit AFTER all assessments have been performed or at a time thereafter during an unscheduled visit. If database lock occurs prior to Day 180, the investigator, subjects, and site personnel will be remained blinded until the Day 180 Visit.
- ^f Informed consent at Screening will address activities up through Day 180 Visit. Informed consent at Day 180 Visit will address the classification of subjects into Categories I, II, and III and activities and assessments that they will undergo.
- ^g Including XIAFLEX as a concomitant medication; the use of the word 'prior' refers to the period between the last visit from the previous Phase 3 clinical study through the signing of informed consent in the EN3835-304 study; not applicable to subjects who sign consent for this study on the same day that they complete the EN3835-302/303 study.
- ^h Serum pregnancy test occurs on Screening visit (carried over from Day 71/EOS visit of EN3835-302/303); urine pregnancy test on Day 180 Visit and, if deemed necessary, at an Unscheduled Visit.
- ⁱ Subject assessments should be completed independently and prior to Investigator assessments at each visit.
- ^j Assessment made via photographs.
- ^k Assessment of each of the 2 buttocks independently.

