6.3.1.2. Concomitant Status of Medication for Completely Unknown Start Date

The following rules will apply in cases where start date of concomitant medication is completely unknown:

- If the medication onset date is unknown and the end date is after the informed consent date or ongoing, then the medication will be considered as concomitant.
- If the medication onset date is unknown and the end date is before the informed consent, then the medication will not be considered as concomitant.
- If both the start and end dates are unknown (or medication is ongoing), then the medication will be considered as concomitant, following the worst-case principle.

If the medication onset date is partly present and month/year is prior to the informed consent, then the medication will not be considered as concomitant.

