7.5. Prior and Concomitant Medications/Procedures

Prior and concomitant medications will be summarized using frequency counts and percentages by active ingredient within each ATC, with ATC and active ingredients ordered alphabetically. Multiple use of the same medication by a subject will be counted only once.

Prior and concomitant medications will be summarized for the Day-180 Observational Population and Prior to Day 180 Population by treatment arm (ie, CCH 1.68 mg, Placebo, and Overall). Concomitant medications will be summarized for the Open-label Observation Population by Subject Category (ie, Category I, II, III, and Overall), and OLR Population by Subject Category (ie, Category I, II, and Overall).

The subject listings of prior and concomitant medications/procedures will be presented for All Subjects and for Prior to Day 180 Observational Population will be presented separately.

The separate listings of prior and concomitant medications/procedures and EFP/Cellulite will also be provided for All Subjects as well as for Prior to Day 180 Observational Population.

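### Concomitant medication is defined by start date, so drugs known to have begun before consent and continued are left out of the open-label tables, while the same drugs with an unknown start are counted

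*SAP*

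**What the plan says.** **Definitions (SAP 4.3).** A prior medication is "any medication taken from the last visit of the double-blind study through the signing of informed consent form at Screening A". For the other class the section says: "A concomitant medication is any medication starting on or after the informed consent form at Screening A is signed for this study". The first definition turns on when the drug was taken, the second on when it was begun.

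**Date rules (SAP 6.3.1.2).** For a completely unknown start date the condition for counting the drug as concomitant reads: "If the medication onset date is unknown and the end date is after the informed consent date or ongoing". If both dates are unknown, the drug is also concomitant, on a worst-case argument. A start date that is "partly present and month/year is prior to the informed consent, then the medication will not be considered as concomitant". That last rule does not look at the end date or at whether the drug is ongoing.

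**Tables (SAP 7.5).** For the first period: "Prior and concomitant medications will be summarized for the Day-180 Observational Population and Prior to Day 180 Population by treatment arm". For the open-label period: "Concomitant medications will be summarized for the Open-label Observation Population by Subject Category (ie, Category I, II, III, and Overall), and OLR Population". No prior-medication table is planned for the Open-label Observation or OLR Populations. Prior and concomitant medications are both listed for all subjects.

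**Schedule footnote (SAP Table 1, footnote g; repeated under Tables 2 to 4).** The word prior is said to be "not applicable to subjects who sign consent for this study on the same day that they complete the EN3835-302/303 study".

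**The concern.** A concomitant medication table normally shows what subjects were taking while under observation. Under section 4.3 it shows only what they began after signing consent at Screening A. A long-term drug begun before that date and taken throughout, including on the days of retreatment injections, is not concomitant if its start is known or partly known.

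The populations affected are the ones used for long-term safety and for safety after retreatment, both primary objectives. A reader of an adverse event table may turn to the medication table for context. Low-dose aspirin shows why this matters. Section 3.10.1 prohibits anticoagulants and antiplatelet agents during retreatment because of bruising but permits aspirin up to 150 mg per day. Section 3.11.1 makes bruising remote from the injection site an adverse event of special interest. Permitted aspirin already in use at consent, with a recorded start date, would be absent from the OLR table. Because it is permitted, it would not appear as a deviation either. The same holds for other long-term drugs, such as hormonal contraceptives, which section 3.2.1.5 names as an accepted method for retreated subjects.

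**Working it through.** There is no figure to reproduce, so the check applies the rules in turn to one case: a drug begun before Screening A consent and still taken after it.

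| What is known of the start date | Rule that applies | Class | In the Open-label Observation and OLR concomitant tables? |
|---|---|---|---|
| Full date, before consent | 4.3 definition | Not concomitant | No |
| Month and year, before consent | 6.3.1.2 partial-date rule | Not concomitant | No |
| Nothing; drug ongoing or ended after consent | 6.3.1.2 unknown-start rule | Concomitant | Yes |
| Nothing; end date also unknown | 6.3.1.2 worst-case rule | Concomitant | Yes |

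The drug use is the same in the first three rows. Only the completeness of the start date differs, and the better-documented records are the ones left out.

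**Does another table catch the omitted drugs?** Under 4.3 such a drug fits the prior definition if it was taken between the last double-blind visit and consent. Section 7.5 tabulates prior medications for the Day-180 Observational and Prior to Day 180 Populations, by double-blind arm. It plans no prior table by subject category and none for retreated subjects. The omitted drugs therefore have no summary in the two open-label populations.

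**Are the records lost?** No. Section 3.10 has medications recorded from the last double-blind visit, 7.5 lists them for all subjects, and 6.1 promises listings of all CRF data.

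**Same-day consenters.** For a subject who consents on the day she completes the double-blind study, the prior window in 4.3 shrinks to that day. On the wording of 4.3 alone, a drug taken that day is prior. Footnote g says the term does not apply to her. The two texts leave it unclear whether the drug is classed as prior.

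**Which drugs are unaffected?** The cut-off is Screening A consent, not retreatment. A drug begun after that consent and before the first retreatment injection is concomitant and does reach the OLR table. Section 7.5 states no time window for that table, so it also admits a drug begun after consent and stopped before retreatment.

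**The case against.** The case against giving this much weight is strong on consequence, and most of it stands.

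- **Prohibited drugs.** A reader might infer that anticoagulant or antiplatelet use during retreatment would go unseen. The SAP does not support that. Section 3.2.2.4, criterion 3, excludes such subjects from retreatment, apart from aspirin up to 150 mg daily. Section 4.2 names prohibited medications as a deviation type, drawn from eCRF data and monitoring reports without reference to the concomitant class. Section 7.2 lists all deviations.
- **Every long-term drug.** A reader might infer that all drugs ongoing at consent are dropped. They are not: those with a completely unknown start date are counted. The loss is confined to known or partly known starts before consent.
- **Neither class for same-day consenters.** This is tempting, but it rests on a footnote to a schedule of events. Section 4.3 has no such exception. The text supports ambiguity only.
- **Purpose of the OLR table.** Section 7.5 does not say that the table is limited to drugs taken during retreatment. A window starting at the first retreatment injection would be an improvement rather than the repair of a stated error.
- **Likely intent.** The worst-case wording in 6.3.1.2 suggests that ongoing drugs were meant to be counted, and that 4.3 and the partial-date rule are slips of wording.

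None of this removes the contradiction. A programmer following 4.3 and the partial-date rule as written would still produce tables that omit these drugs.

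**Conclusion.** The point holds as an internal contradiction between section 4.3 and the partial-date rule on one side and the unknown-start rule in 6.3.1.2 on the other. It produces an undercount in the concomitant medication tables for the Open-label Observation and OLR Populations.

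The direction is certain for the drugs concerned: those with a known or partly known start before Screening A consent and use continuing after it. The size is not. The SAP expects about 420 subjects treated with CCH to remain in observation, but says nothing on how many were taking such drugs or how complete their start dates are. No count can be derived.

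Severity is minor. The tables are descriptive, the records remain in the listings, and no efficacy, adverse event, immunogenicity or population definition uses the concomitant class. The conclusion assumes that the tables are programmed from the SAP text as it stands and that no programming specification, which is not at hand, overrides it.

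**What to change.** 1. In 4.3, define concomitant as any medication taken on or after Screening A consent, including one begun earlier that is ongoing at consent or ends after it. State that a drug may be both prior and concomitant.
2. In 6.3.1.2, let the partial-date rule exclude a drug only if it also stopped before consent. This brings it into line with the unknown-start rule.
3. State in 4.3 how drugs in use are classed for subjects who consent on the day they complete the double-blind study, and reconcile this with footnote g and its repeats.
4. Optionally, since the OLR Population is used for data after retreatment, tabulate for it the drugs taken on or after the first retreatment injection, including those ongoing then.

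The cost is SAP wording and a small programming change. The existing rules already rely on start and end dates and ongoing status, so no new data are needed.

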4.4. Efficacy Parameters

Cellulite assessments using the PR-PCSS, CR-PCSS, S-GAIS, PR-CIS, Subject satisfaction with cellulite treatment assessment, and SSRS will be performed on the eligible buttock(s).

If both the buttocks are eligible then the assessments using the PR-PCSS, CR-PCSS, and S-GAIS will be evaluated separately for each buttock, and assessments using PR-CIS, Subject satisfaction with cellulite treatment assessment, and SSRS will be evaluated for two buttocks.

4.4.1. Change from Baseline in Cellulite Severity Scale (PR-PCSS and CR-PCSS)

The change from Day 1 of the double-blind study for PR-PCSS and CR-PCSS is defined as PR-PCSS and CR-PCSS score at respective visit minus PR-PCSS and CR-PCSS score at Day 1 of the double-blind study.

The change from Day 71/EOS of the double-blind study for PR-PCSS and CR-PCSS is defined as PR-PCSS and CR-PCSS score at respective visit minus PR-PCSS and CR-PCSS score at Day 71/EOS of the double-blind study.

The change from Day 1 of retreatment period of this study for PR-PCSS and CR-PCSS is defined as PR-PCSS and CR-PCSS score at respective visit minus PR-PCSS and CR-PCSS score at Day 1 of retreatment period of this study.

4.4.2. Reduction / Improvement of Response in Cellulite Severity Scale (PR-PCSS and CR-PCSS)

Reduction of Response will be assessed separately for prior to retreatment (including Through Day 180 Observational Period) and after retreatment. Refer below Table 13 for definitions of reduction of response:

Table 13: Reduction of Response

Variables	Prior to Retreatment (including Through Day 180 Observational Period)	After Retreatment
Reduction of Response	Worsening of cellulite severity improvement on PR-PCSS or CR-PCSS ratings in this study prior to retreatment compared to the score at Day 71/EOS (or Day 1) in the double-blind study. This reduction is also referred as a Partial Loss of Response.	Worsening of cellulite severity improvement on PR-PCSS or CR-PCSS ratings during the observation phase after retreatment compared to the score at Day 71/End of Treatment Session in the open-label treatment phase.
2-level Reduction	Worsening of cellulite severity improvement at least by 2-level on PR-PCSS or CR-PCSS ratings in this study prior to retreatment, compared to the score at Day 71/EOS (or Day 1) in the double-blind study (ie, change from baseline PR-PCSS and/or CR-PCSS rating of 2, 3, or 4)	Worsening of cellulite severity improvement at least by 2-level on PR-PCSS or CR-PCSS ratings during the observation phase after retreatment compared to the score at Day 71/End of Treatment Session in the open-label treatment phase (ie, change from baseline PR-PCSS and/or CR-PCSS rating of 2, 3, or 4)
1-level Reduction	Worsening of cellulite severity improvement by only 1-level on PR-PCSS or CR-PCSS ratings in this study after retreatment compared to the score at Day 71/EOS (or Day 1) in the double-blind study (ie, change from baseline PR-PCSS and/or CR-PCSS rating of 1)	Worsening of cellulite severity improvement only by 1-level on PR-PCSS or CR-PCSS ratings during the observation phase after retreatment compared to the score at Day 71/End of Treatment Session in the open-label treatment phase (ie, change from baseline PR-PCSS and/or CR-PCSS rating of 1)
Composite Reduction	Composite Reduction will be assessed using both the subject PR-PCSS responder classification and investigator CR-PCSS responder, where both the scales have same level of reduction. If the classification is missing for 1 or both components (ie, the PR-PCSS component or the CR-PCSS component), then the composite responder classification is missing for that visit.	
2-level Composite Reduction	Worsening of cellulite severity improvement by at least 2-level on both PR-PCSS and CR-PCSS ratings compared to the score at Day 71/EOS (or Day 1) in the double-blind study.	Worsening of cellulite severity improvement by at least 2-level on both PR-PCSS and CR-PCSS ratings compared to the score at Day 71/End of Treatment Session in the open-label treatment phase.
1-level Composite Reduction	Worsening of cellulite severity improvement by only 1-level on both PR-PCSS and CR-PCSS ratings compared to the score at Day 71/EOS (or Day 1) in the double-blind study.	Worsening of cellulite severity improvement by only 1-level on both PR-PCSS and CR-PCSS ratings compared to the score at Day 71/End of Treatment Session in the open-label treatment phase.
Time to Composite Reduction of Response by 2-level	Number of days from the time of assessing composite improvement in cellulite severity on PR-PCSS and CR-PCSS at Day 71/EOS (or Day 1) in the double-blind study to the study visit prior to retreatment at which at least 2 level of worsening of response in both PR-PCSS and CR-PCSS ratings is observed for the first time.	Number of days from the time of assessing composite improvement in cellulite severity on PR-PCSS and CR-PCSS at Day 71/End of Treatment Session in the open-label treatment phase to the study visit during observation phase after retreatment at which at least 2 level of worsening of response in both PR-PCSS and CR-PCSS ratings is observed for the first time.
Time to Composite Reduction of Response by 1-level	Number of days from the time of assessing composite improvement in cellulite severity on PR-PCSS and CR-PCSS at Day 71/EOS (or Day 1) in the double-blind study to the study visit prior to retreatment at which only 1-level of worsening of response in both PR-PCSS and CR-PCSS ratings is observed for the first time.	Number of days from the time of assessing composite improvement in cellulite severity on PR-PCSS and CR-PCSS at Day 71/End of Treatment Session in the open-label treatment phase to the study visit during observation phase after retreatment at which only 1-level of worsening of response in both PR-PCSS and CR-PCSS ratings is observed for the first time.

Table 13: Reduction of Response (Continued)

Variables	Prior to Retreatment (including Through Day 180 Observational Period)	After Retreatment
Complete Loss of Response	Worsening of cellulite severity improvement on PR-PCSS and CR-PCSS ratings in this study prior to retreatment compared to the score at Day 71/EOS in the double-blind studies, where cellulite severity returns to baseline levels of the double-blind studies (ie, Day 1 of the double-blind studies) or worse.	Worsening of cellulite severity improvement on PR-PCSS and CR-PCSS ratings compared to the score at Day 71/End of Treatment Session in the open-label treatment phase, where cellulite severity returns to baseline levels of the retreatment phase (ie, Day 1 of the open-label retreatment phase) or worse.
Time to Complete Loss of Response	Number of days from the time of assessing composite improvement in cellulite severity on PR-PCSS and CR-PCSS at Day 71/EOS in the double-blind study to the study visit prior to retreatment at which the complete loss of response in both PR-PCSS and CR-PCSS is observed.	Number of days from the time of assessing composite improvement in cellulite severity on PR-PCSS and CR-PCSS at Day 71/End of Treatment Session in the open-label treatment phase to the study visit during observation phase after retreatment at which the complete loss of response in both PR-PCSS and CR-PCSS is observed.
2-level Improvement	Improvement in cellulite severity at least by 2 levels on PR-PCSS or CR-PCSS ratings from Day 1 of double-blind study (ie, change from baseline PR-PCSS and/or CR-PCSS rating of -2, or -3).	Improvement in cellulite severity at least by 2 levels on PR-PCSS or CR-PCSS ratings after receiving the retreatments compared to the corresponding rating at Day 1 of the Treatment Session of this study (ie, change from baseline PR-PCSS and/or CR-PCSS rating of -2, or -3).
1-level Improvement	Improvement in cellulite severity at least by 1 levels on PR-PCSS or CR-PCSS ratings from Day 1 of double-blind study (ie, change from baseline PR-PCSS and/or CR-PCSS rating of -2, or -3).	Improvement in cellulite severity at least by 1 levels on PR-PCSS or CR-PCSS ratings after receiving the retreatments compared to the corresponding rating at Day 1 of the Treatment Session of this study (ie, change from baseline PR-PCSS and/or CR-PCSS rating of -2, or -3).
2-level Responder	Improvement in the PR-PCSS or CR-PCSS ratings of at least 2 levels compared to the ratings at Day 1 of double-blind study.	Improvement in the PR-PCSS or CR-PCSS ratings of at least 2 levels compared to the ratings at Day 1 of the Treatment Session of this study.
1-level Responder	Improvement in the PR-PCSS or CR-PCSS ratings of at least 1 levels compared to the ratings at Day 1 of double-blind study.	Improvement in the PR-PCSS or CR-PCSS ratings of at least 1 levels compared to the ratings at Day 1 of the Treatment Session of this study.
2-level Composite Responder	Subject who is both 2-level PR-PCSS responder and a 2-level CR-PCSS responder.	
1-level Composite Responder	Subject who is both 1-level PR-PCSS responder and a 2-level CR-PCSS responder.	

Note: If the classification is missing for 1 or both components (ie, the PR-PCSS component or the CR-PCSS component), then the composite responder classification is missing for that visit.

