Upon completion and unblinding of the double-blind studies EN3835-302/303 (see [Figure 1](#)), subjects who received placebo during the double-blind studies will be discontinued, and subjects who received active CCH will be classified into one of three Categories:

- Category I: 1-Level Composite Responders
- Category II: 2-Level Composite Responders
- Category III: Non-Composite Responders

Composite response will be assessed using both the subject PR-PCSS (Patient Reported Photonumeric Cellulite Severity Scale) responder classification and investigator CR-PCSS (Clinician-Reported Photonumeric Cellulite Severity Scale) responder classification, where same level of improvement is observed by both the scales in the same buttock (eg, for 2 level composite improvement – the improvement in response of at least 2-level should be observed in both PR-PCSS and CR-PCSS for the same buttock).

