The Category II subjects that have not shown at least 1-level composite reduction AND/OR have a buttock that has maintained at least a 2-level composite response (ie, have maintained a successful response), and/or Category I and/or Category II subjects who are eligible for a retreatment course but opted not to receive retreatment will have cellulite assessments at Months 12, 18, 24, and 36 from Day 71 of the double-blind study. If the subject's buttock(s) become eligible for retreatment based on the ratings during an observational visit and if they have not already received a course of retreatment in this study, then they will be offered one course of retreatment for the eligible buttock(s); one course of concurrent treatment for up to two eligible buttocks.

If a treatment period overlaps a scheduled observational visit, the observational visit will be skipped, and the subject will re-enter the observational schedule at the next interval visit. For example, if a subject initiated retreatment on Day 351 (which would then be Treatment Visit 1), the treatment period would proceed for approximately 71 days until Day 421 (Treatment Visit 4) and the Observational Visit at Day 360 would be skipped; the subject's next observational visit would be Day 540.

[figure not shown]

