7.6.2. Reduction of response using PR-PCSS and CR-PCSS Prior to Retreatment

The proportion of subjects or buttocks with reduction of response (refer to section 4.4.1) will be summarized using frequency counts and percentages using TRR Population Before Retreatment and OLNLR Population subject category (ie, Category I and II, and Overall) and treatment area (ie, left and/or buttock) at the following visits prior to retreatment: Day 180, Month 12, 18, 24, and 36 where reduction of response is assessed.

The proportions will be computed based upon number of subjects within each category and treatment area remains not-retreated prior to that visit.

The following efficacy end points for reduction of response will be summarized:

- Proportion of subjects with 2-level composite reduction
- Proportion of subjects with 1-level composite reduction
- Proportion of subjects with complete loss of response

The time to composite reduction of response (ie, by 1-level and 2-level separately) and time to complete loss of response (refer to section 4.4.1 for derivation) will be summarized descriptively using TRR Population Before Retreatment and OLNLR Population.

The listings of cellulite PR-PCSS and CR-PCSS severity ratings will be provided for All Subjects prior to retreatment.

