7.6.3. Reduction of response using PR-PCSS and CR-PCSS after Retreatment

The proportion of subjects with reduction of response (refer to section 4.4.1) will be summarized using frequency counts and percentages using TRR Population after Retreatment by subject category (ie, Category I and II, and Overall) and treatment area (ie, left and/or buttock) at all observation visits after retreatment where cellulite assessments has been performed.

The proportions will be computed based upon number of subjects within each category and treatment area retreated prior to that visit.

The following efficacy end points for reduction of response will be summarized:

- Proportion of subjects with 2-level composite reduction
- Proportion of subjects with 1-level composite reduction
- Proportion of subjects with 2-level reduction on either scale
- Proportion of subjects with 1-level reduction on either scale
- Proportion of subjects with complete loss of response

The time to composite reduction of response (ie, by 1-level and 2-level separately), time to partial response and time to complete loss of response (refer to section 4.4.1 for derivation) will be summarized descriptively using TRR Population after Retreatment.

The listings of cellulite PR-PCSS and CR-PCSS severity ratings will be provided for subjects in OLR Population after Retreatment.

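### Before retreatment, section 7.6.2 lists and times only events that need both scales to worsen, so a composite response that ends through one scale, or through unequal worsening, is counted as a non-event

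*SAP*

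**What the plan says.** **Response.** SAP section 3.1 defines composite response as one "where same level of improvement is observed by both the scales in the same buttock". Table 13 (section 4.4.2) agrees for the 2-level case: "Subject who is both 2-level PR-PCSS responder and a 2-level CR-PCSS responder".

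**Reduction.** Table 13 requires both scales for a composite reduction, "where both the scales have same level of reduction". The 2-level version is "Worsening of cellulite severity improvement by at least 2-level on both PR-PCSS and CR-PCSS ratings". The 1-level version is "Worsening of cellulite severity improvement by only 1-level on both PR-PCSS and CR-PCSS ratings", that is, exactly one level on each. The matching time variables and complete loss of response also need both scales.

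**Either-scale reduction.** The first rows of Table 13 define a reduction on one scale or the other, both before and after retreatment. The pre-retreatment form is also given the name partial loss.

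**What is reported.** Before retreatment, section 7.6.2 lists three endpoints: 2-level composite reduction, "Proportion of subjects with 1-level composite reduction", and complete loss. It times only the composite reductions and complete loss. After retreatment, section 7.6.3 lists the same three and adds the either-scale rows, for example "Proportion of subjects with 1-level reduction on either scale".

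**The concern.** A state that needs two conditions ends when either one fails. The events listed before retreatment need both scales to worsen, and the 1-level event needs them to worsen by the same amount. That leaves two kinds of buttock that are no longer composite responders yet register no event:

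- one scale has fallen back and the other has held;
- both scales have fallen by unequal amounts, such as one level and two levels, and have not both returned to the Day 1 level.

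Time to reduction of response is the only secondary objective (section 2.2), and section 3.6 calls the sample adequate for it. A durability table that leaves these buttocks in the denominator as non-events will look better than the composite response it is meant to follow. The either-scale rows appear only after retreatment, so the two periods cannot be compared on the same endpoints.

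**Working it through.** The SAP states no figure for this point, so there is none to reproduce. The check applies the Table 13 rules to every possible score pair.

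**Inputs.** Both scales run from 0 to 4 (Tables 6 and 7). Improvement is the Day 1 score minus the visit score. Worsening is the visit score minus the Day 71 score, with Day 71 as reference (Table 17). Pairs are written PR/CR. The Day 1 scores are assumptions. Table 13's row for the 1-level composite responder pairs a 1-level PR with a 2-level CR response; I read it as 1-level on both, as section 3.1 implies.

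**Worked case.** Day 1 = 3/3, Day 71 = 1/1, later visit = 3/1.
- Improvement at the visit: 3−3 = 0 and 3−1 = 2, so not a composite responder at any level.
- Worsening from Day 71: 3−1 = 2 and 1−1 = 0, so no 1-level reduction, no 2-level reduction and no complete loss.

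**Day 1 = 3/3, Day 71 = 1/1 (2-level response).** There are 5 × 5 = 25 later pairs.
- Still a 2-level response (both scores at most 1): 2 × 2 = 4. No longer one: 25 − 4 = 21.
- Captured as 1-level composite reduction: 2/2 only, 1 pair.
- Captured as 2-level composite reduction: both scores 3 or 4, 4 pairs. Complete loss picks out the same 4.
- Uncaptured: 21 − 5 = **16**. Of these, 12 have only one scale worse (2 × 2 × 3) and 4 are unequal (2/3, 2/4, 3/2, 4/2).

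**Day 1 = 3/3, Day 71 = 2/2 (1-level response).**
- Still a 1-level response (both scores at most 2): 3 × 3 = 9. No longer one: 25 − 9 = 16.
- Captured: both scores 3 or 4, 4 pairs, all of them complete loss.
- Uncaptured: 16 − 4 = **12**, all with only one scale worse.

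**Wider enumeration, Day 1 scores of 3 or 4 on each scale (assumed).**

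| Response at Day 71 | States no longer at that level | Meet no both-scale endpoint | One scale only / unequal |
|---|---|---|---|
| At least 2-level | 456 | 320 (70%) | 216 / 104 |
| 1-level | 299 | 220 (74%) | 194 / 26 |

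An either-scale rule picks up all 456 and all 299. In the 2-level set, 10 further states count as a reduction although the 2-level response is still held.

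**Illustration with assumed rates.** Take a buttock exactly at threshold on both scales. Each scale worsens with probability p, and the latent correlation is r. Then P(both) is the bivariate normal probability, P(either) = 2p − P(both), and the missed share is 1 − P(both)/P(either).
- p = 0.2, r = 0.5: P(both) = 0.087, P(either) = 0.400 − 0.087 = 0.313, missed share = 1 − 0.087/0.313 = 0.72.
- Over p = 0.1 to 0.4 and r = 0.3 to 0.9, the missed share runs from 0.88 (p = 0.1, r = 0.3) to 0.30 (p = 0.4, r = 0.9).

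P(both) includes unequal worsening, so for 2-level responders the true gap is at least this large.

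**The case against.** **The SAP does not use a both-scale rule throughout.** This stands. Table 13 defines either-scale reduction. Section 7.6.2 opens with the general term, and Table 17 times reduction to its first detection without asking for both scales. But the endpoints that 7.6.2 then lists and times are all both-scale, so the defect is a mismatch between the definitions and the list.

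**Other tables show part of the picture.** Section 7.6.1 tabulates each scale by buttock and visit, so a fall in PR-PCSS would be visible there. Separate tables cannot give the joint status of a buttock. Table 16 mentions a responder analysis for the not-retreated population, but section 7.6 sets out no PR-PCSS/CR-PCSS version of it, and that population omits everyone later retreated. Section 7.6.4 gives composite-responder proportions only at Days 22, 43 and 71 of retreatment. The table shells are in a separate module that is not available, so all that can be said is that the SAP text does not list the analysis.

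**Requiring agreement is defensible.** On five-level ratings, an either-scale rule will count some one-rater fluctuation as loss. The SAP also plans confirmation visits for composite worsening. This argues for keeping the planned endpoints and against replacing them.

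**Two stronger readings are tempting.** A reader might infer that such buttocks are reported as having kept their response, since section 3.1.2 describes certain Category II subjects as those who "have maintained a successful response". That passage concerns follow-up and eligibility, and no endpoint in 7.6.2 carries that label; the buttock is simply a non-event. A reader might also infer that the rule always lengthens durability. It does not: a fall from 3 levels of improvement to 2 on both scales counts as a 1-level composite reduction while the 2-level response is still held.

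**Conclusion.** The point holds for section 7.6.2. Before retreatment, a buttock whose composite response ended through one scale, or through unequal worsening that stops short of complete loss, meets none of the listed or timed endpoints. The either-scale measure that would catch it is defined in Table 13 and reported in 7.6.3, but is not listed before retreatment.

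For buttocks at the response threshold on Day 71, this overstates durability. From a Day 1 of 3/3, the listed endpoints miss 16 of 21 lost pairs (Day 71 at 1/1) and 12 of 16 (Day 71 at 2/2). These count possible scores with equal weight, rest on an assumed Day 1 score and are not expected patient rates. The 30% to 88% missed share rests on assumed worsening rates and correlations. The direction of the error is not settled for buttocks above the threshold on Day 71. The study is a descriptive extension with safety and immunogenicity as primary objectives, so the gap affects the reading of the secondary objective only.

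**What to change.** In section 7.6.2, keep the planned endpoints and add, per buttock and visit:

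1. the 1-level and 2-level either-scale reduction rows already used in 7.6.3;
2. the proportion no longer a composite responder against double-blind Day 1 at the level held on Day 71, with time to that event. This means below 2 levels on either scale for buttocks with at least a 2-level response, and below 1 level on either scale for those with a 1-level response.

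Report these alongside composite reduction, not in place of it. The retreatment criteria are not touched.

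The cost is SAP wording and a few more table rows; both ratings are already scheduled at the visits concerned. The added durability figure will be less favourable and more sensitive to fluctuation in a single rater's score, which is a reason to show both measures together.
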